2.5.4 Handling of missing values not related to intercurrent event

No imputation will be made.

2.5.5 Sensitivity analyses

Not Applicable

2.5.6 Supplementary analyses

Commercially Confidential Information

2.6 Safety analyses (Safety analysis set)

All safety analyses will be performed using the SAF. All listings and tables will be presented by treatment group.

2.6.1 Adverse events (AEs)

AEs and serious adverse events (SAEs) will be monitored, treated and appropriately recorded by the Investigator from Day 1 until EOS (Day 56).

The number (and percentage) of participants with adverse events will be tabulated in the following ways:

- by Primary system organ class and preferred term
- by Primary system organ class and preferred term and maximum severity

A participant with multiple AEs within a primary system organ class is only counted once towards the total of the primary system organ class. If a participant reported more than one adverse event with the same preferred term, the adverse event with the greatest severity will be presented.

Summaries will also be presented for AEs by severity (toxicity grade), for study treatment related AEs, for AEs duration (start and end dates) or if the event is ongoing, of not recovered/not resolved, for whether an AE constitutes an SAE and for its outcome (i.e. recovery status or whether it was fatal).

The most common adverse events reported ($\geq z\%$ in any group for each preferred term in the table by SOC and PT) will be presented in the clinical study report by descending frequency according to its incidence in overall group starting from the most common event. Here threshold value z is set to 5 (%) but it may be updated following review of the dry run outputs.

For the legal requirements of ClinicalTrials.gov, two required tables on treatment emergent adverse events which are not serious adverse events with an incidence greater than 5% and on treatment emergent serious adverse events and SAE suspected to be related to study treatment will also be provided by system organ class and preferred term on the safety set.

If for a same participant, several consecutive AEs (irrespective of study treatment causality, seriousness and severity) occurred with the same SOC and PT:

- a single occurrence will be counted if there is ≤1 day gap between the end date of the preceding AE and the start date of the consecutive AE
- more than one occurrence will be counted if there is >1 day gap between the end date of the preceding AE and the start date of the consecutive AE

For occurrence, the presence of at least one SAE / SAE suspected to be related to study treatment / non SAE must be checked in a block e.g., among AE's in a \leq 1 day gap block, if at least one SAE is occurring, then one occurrence is calculated for that SAE.

Separate summaries will be provided for ABO809 related AEs, SAEs, adverse events of special interest (AESIs) and deaths.

No statistical analysis will be performed for safety and tolerability evaluation.

2.6.1.1 Adverse events of special interest / grouping of AEs

The number and percentage of participants with these special AEs will be tabulated. In addition, listings of related adverse events will be provided.

All clinical signs and symptoms associated with *Cryptosporidium* infection will be characterized as AEs. The Investigator will report AEs through Day 56 (EOS) and from EOS through 12 months after ABO809 administration and follow-up accordingly; These include:

- Gastroenteritis in the absence of *Cryptosporidium* infection: In the event of gastroenteritis in the absence of *Cryptosporidium* infection, the event will be considered an AEs. The Investigator will investigate other potential causes of diarrhea, including infectious diarrhea and manage participant's care according to local standards.
- Extraintestinal cryptosporidiosis: *Cryptosporidium* infection involving the biliary tract, lungs, liver, pancreas, or other organs will be considered AEs.
- **Persistent or recurrent cryptosporidiosis:** Persistent clinical symptoms after administration of standard of care (e.g. Nitazoxanide, oral or IV hydration and electrolyte replacement), or after initial resolution of *Cryptosporidium* oocysts in the stool and/or diarrheal symptoms, will be considered an AEs.
- **Persistent** *Cryptosporidium* **shedding:** Persistent detection of *Cryptosporidium* oocysts in stools after treatment with nitazoxanide will be considered an AEs.
- **Dehydration:** Moderate or severe dehydration, as defined below will be considered an AESI.
 - **Mild:** dry mucous membranes; diminished skin turgor; increased oral fluids are indicated.
 - Moderate: IV fluids are indicated.
 - Severe: hospitalization is indicated, or it is considered to have life-threatening consequences; or an urgent intervention is indicated.
- **Non-intestinal sequelae:** Development of new onset non-intestinal symptoms, including eye pain or joint pain, will be considered AEs.

2.6.2 **Deaths**

The number of deaths resulting from SAEs suspected to be related to study treatment and number of deaths resulting from SAEs irrespective of causality will be provided by SOC and PT.

2.6.3 Laboratory data

Clinical laboratory data will include chemistry, hematology and urinalysis results up to EOS. All laboratory values will be converted into International System of Units (SI) units. Grading will be assessed using the U.S. Food and Drug Administration's (FDA) "Toxicity Grading Scale for Healthy Adult and Adolescent Volunteers Enrolled in Preventive Vaccine Clinical Trials (2007)". For AEs that are not contained in the "Toxicity Grading Scale for Healthy Adult and Adolescent Volunteers Enrolled in Preventive Vaccine Clinical Trials (2007)", Mild/Moderate/Severe will be used as categorization. Additional information is provided in Section 5.3.

Descriptive statistics (means, medians, standard deviations, ranges) by time point will be generated for all clinical laboratory tests performed (actual values and changes from baseline) for three groups of laboratory tests by laboratory test and treatment group. Change from baseline

will only be summarized for participants with both baseline and post baseline values and will be calculated as:

change from baseline = post baseline value - baseline value

Box plot for lab parameters will also be provided by timepoint and treatment group as applicable.

2.6.4 Other safety data

Boxplots to visualize trends in longitudinal safety data (vitals, ECG) will be created.

2.6.4.1 ECG and cardiac imaging data

The following quantitative variables will be summarized: heart rate, RR interval, PR interval, QRS interval, QT interval, QTcF (QT interval corrected for heart rate according to Fredericia) and optionally QTcB (QT interval corrected for heart rate according to Bazett). Summary statistics for change from baseline will be presented for ECG variables by timepoint and treatment group.

ECG parameters will be summarized categorically by computing the number and percentage of participants at each time point and at the maximum post baseline value with following:

- QT, QTcF, or QTcB
 - >450 and ≤480 ms
 - >480 and ≤500 ms
 - >500 ms
 - Increase from Baseline of ≥30 ms to <60ms
 - Increase from Baseline of >60 ms
- HR
 - Increase from baseline >25% and to a value >100 bpm
 - Decrease from baseline >25% and to a value <50 bpm
- PR
 - Increase from baseline >25% and to a value >200 ms
 - New value of >200 ms
- QRS
 - Increase from baseline >25% and to a value >120 ms
 - >120 ms

All ECG data will be listed; notably all newly occurring or worsening abnormalities as compared with baseline will be provided, abnormal values will be flagged, and the overall interpretation of abnormality will be presented.

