As per Section 4.6, during a Public Health emergency as declared by Local or Regional authorities i.e. pandemic, epidemic, or natural disaster, that limits or prevents on-site study visits, alternative methods of providing continuing care may be implemented by the investigator as the situation dictates. If allowable by a local Health Authority and depending on operational capabilities, phone calls, virtual contacts (e.g. tele consult) or visits by site staff/home nursing staff to the participant home, can replace on-site study visits, for the duration of the disruption until it is safe for the participant to visit the site again.

Participants may be asked to check-in to the study site prior to Day 1 to undergo additional COVID-19 precaution procedures.

Table 8-1 Assessment Schedule

Period	Scree	ning	Treatment			ln-	Patie	nt Fo	llow	-Up						Out	tpatient	t Follow	-Up		
Visit Name	Screening	Baseline	Treatment			lnį	patie	nt Fo	llow-	Up			0	utpat	ient F Visit	ollow	-Up	Safet	y Follo Call	w-Up	End of Study Call
Visit Number	1	2	101	102	103	104	105	106	107	108	109	110	111	112	113	114	115	116	117	118	199
Days	-28 to -2	-1	1	2	102 103 104 105 106 107 108 109 1 2 3 4 5 6 7 8 9 1								14	17	21	24	28	35	42	49	56
Informed consent	Х																				

Understanding of Cryptosporidium Infection & Transmission Quiz	S											
Medical history/current medical conditions	x											
Physical Examination	S	S					S			S		

Period	Scree	ning	Treatment			ln-	Patie	nt Fo	llow-	·Up						Ou	tpatien	t Follow	-Up		
Visit Name	Screening	Baseline	Treatment			lnį	patie	nt Fo	llow-	Up			0	utpat	ient F Visit	ollow	v-Up	Safet	y Follo Call	w-Up	End of Study Call
Visit Number	1	2	101	102	103	104	105	106	107	108	109	110	111	112	113	114	115	116	117	118	199
Days	-28 to -2	-1	1	2	3	4	5	6	7	8	9	10	14	17	21	24	28	35	42	49	56
Inclusion / Exclusion criteria	S	S																			
Demography	Х																				
Alcohol Test, Drug Screen, and Cotinine Test	S	S																			
SARS-CoV2 Screen	Х	Х																			
Hepatitis screen	S																				
HIV screen	S																				
Thyroid stimulating hormone	Х																				
T4 (Free)	Х																				
Pregnancy ²	Х	Х															Х				
Body Height	Х																				
Body Weight ¹¹	Х	X	X ³	Χ	Х	Х	Х	Х	Х	Х	Х	Х	Х	Х	Х	Х	Х				
Vital Signs ¹¹	Х	X	X ³	Χ	Х	Х	Х	Х	Х	Х	Х	Х	Х	Х	Х	Х	Х				
Electrocardiogram (ECG) ¹¹	Х	Х	X 3									х					Х				
Hematology ¹¹	Χ		X ³									Х					Х				
Clinical Chemistry ¹¹	Х		X ³									х					Х				

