8.4.2 Electrocardiogram (ECG)

All ECGs will be measured after a 10 minute rest in the supine position. The following parameters will be reported: PR interval, QRS duration, heart rate, RR interval, QT interval and QTcF interval.

The Fridericia QT correction formula (QTcF) must be used for clinical decisions: $QTcF = QT/(RR/1s)^{1/3}$

As applicable, QTcF and QTcB may be calculated at the site. Unless auto-calculated by the ECG machine, the Investigator must calculate QTcF at the Screening and/or Baseline visit(s) (as applicable) to assess eligibility and continuation in the study.

Additional, unscheduled, safety ECGs may be repeated at the discretion of the investigator at any time during the study as clinically indicated, e.g. in the case of dehydration.

For any ECGs with participant safety concerns, two additional ECGs must be performed to confirm the safety finding. ECG safety monitoring, or a review process, should be in place for clinically significant ECG findings at baseline before administration of study treatment and during the study.

Clinically significant abnormalities must be recorded on the eCRF as either medical history/current medical condition or adverse event as appropriate.

Amended Protocol Version v02 (Clean)

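### The across-visit ECG row in SAP 2.6.4.1 uses the maximum post-baseline value for every category, which is the wrong extreme for a heart-rate decrease (minor)

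*SAP*

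**What the plan says.** SAP 2.6.4.1 plans a categorical ECG summary giving the number and percentage of participants "at each time point and at the maximum post baseline value with following", followed by a single list of categories. There are thus two levels: a row for each time point, and one row across visits. The maximum is the only across-visit value named; no minimum is defined.

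Most categories in the list are increases or upper limits (QT and QTc, heart-rate increase, PR, QRS). One points the other way: "Decrease from baseline >25% and to a value <50 bpm".

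The QT block is headed "QT, QTcF, or QTcB", so uncorrected QT shares the 450, 480 and 500 ms limits with the corrected intervals. It also shares the change categories, such as "Increase from Baseline of ≥30 ms to <60ms". Protocol 8.4.2 says: "The Fridericia QT correction formula (QTcF) must be used for clinical decisions".

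The same SAP section lists all ECG data, and "abnormal values will be flagged, and the overall interpretation of abnormality will be presented".

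**The concern.** An across-visit row answers the question of how many participants ever met a criterion. For increases and upper limits the maximum answers it, because one qualifying value is enough. For a decrease the maximum answers a different question: how many participants met the criterion at every ECG. Nothing in the section marks the heart-rate decrease as an exception.

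ECG findings are part of a secondary safety endpoint (Protocol section 2; SAP Table 1-1). With about 10 participants per cohort, one participant missing from a count moves a cohort percentage by about 10 points (1/10). Per-visit rows do not directly give an ever-count, and a flagged listing does not correct a table cell.

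Unscheduled ECGs add to this. Protocol 8.4.2 allows them at the investigator's discretion, with dehydration as its example, and requires two further ECGs when an ECG raises a safety concern. SAP 2.6.4.1 does not say whether these enter the visit rows. If they do not, the across-visit row is the only count that could include them.

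The QT block raises a lesser matter. Uncorrected QT lengthens as heart rate falls, so QTc-type limits on QT partly record heart rate.

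**Working it through.** The plan gives no figure for these categories, so there is none to reproduce.

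**Inputs from the documents**
- Decrease rule: more than 25% below baseline and below 50 bpm (SAP 2.6.4.1).
- Baseline: last pre-dose value (SAP 2.1.1).
- Scheduled post-dose ECGs: Day 10 and Day 28, as I read Table 8-1; the Day 1 ECG is pre-dose.
- Eligible pulse: 50 to 90 bpm (Protocol 5.1).
- QTcF = QT/(RR/1 s)^(1/3) (Protocol 8.4.2).

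**Step 1: logic, with no distributional assumption.** With baseline b, a heart rate h qualifies if h < c, where c = min(0.75b, 50). The maximum is below c only if all post-baseline values are below c. The minimum is below c if at least one is.

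| Baseline | c | Post-baseline values | Visit rows | At maximum | At minimum |
|---|---|---|---|---|---|
| 68 | min(51, 50) = 50 | Day 10: 48; Day 28: 64 | Day 10 yes, Day 28 no | 64: no | 48: yes |
| 70 | min(52.5, 50) = 50 | Day 10: 48; Day 28: 49 | both yes | 49: yes | 48: yes |
| 68 | 50 | Day 10: 64; unscheduled: 48; Day 28: 64 | both no | 64: no | 48: yes |

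In the first case the fall is (68 − 48)/68 = 29%. In the third, if visit rows hold scheduled ECGs only, no count in the table records the event.

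**Step 2: how often the row differs.** The documents give no heart-rate variability, so this is an assumed range: mean 60 to 70 bpm, between-person SD 8, within-person SD 5 to 9, independent visit errors, no effect of ABO809, baseline kept to 50 to 90 bpm. A simulation with two post-dose ECGs gave:

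| Mean, within-person SD | One visit row | At minimum (any visit) | At maximum | Maximum/any |
|---|---|---|---|---|
| 70, 5 (lowest) | 0.16% | 0.31% | 0.009% | 2.8% |
| 65, 7 (middle) | 2.0% | 3.8% | 0.23% | 6.1% |
| 60, 9 (highest) | 7.7% | 13.8% | 1.5% | 10.8% |

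For 60 participants the middle case gives 60 × 0.038 = 2.3 expected at the minimum against 60 × 0.0023 = 0.14 at the maximum.

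In the middle case the gap grows with the number of ECGs per participant: 2.0% against 2.0% with one, 3.8% against 0.23% with two, 5.3% against 0.05% with three, and 6.8% against 0.02% with four (minimum against maximum).

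**Step 3: uncorrected QT.** Inverting the protocol's formula, QT = QTcF × (60/HR)^(1/3).
- At 50 bpm the factor is 1.0627, so QT exceeds 450 ms once QTcF exceeds 450/1.0627 = 423.5 ms.
- From 70 to 55 bpm at constant QTcF 410 ms: 410 × 0.9499 = 389.5 and 410 × 1.0294 = 422.1. QT rises 32.6 ms and falls in the 30 to <60 ms category with no change in QTcF.
- In the other direction, QTcF 460 ms at 80 bpm is QT 417.9 ms. The QT row shows nothing, but the QTcF row counts it in the lowest category (above 450 ms).

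**The case against.** The strongest reply is that the section also counts at each time point. With two scheduled post-dose ECGs, the visit rows cover every scheduled observation, so the first participant in the working is counted on Day 10. If every participant had exactly those two ECGs, the ever-count could be recovered as Day 10 plus Day 28 minus the maximum row, since that row is then the number qualifying at both (middle case: 2.0% + 2.0% − 0.23% = 3.8%). Low heart rates are also visible in the flagged listing, the by-visit summaries (which include the minimum, SAP 2.1), the boxplots (SAP 2.6.4) and the separately scheduled pulse data (SAP 2.6.4.2). All of this stands. It does not make the across-visit cell right, and the recovery fails once a participant has a missing or an unscheduled ECG.

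A reader might infer that the plan cannot count bradycardia, or that its tables would report none when it occurred. The documents do not support that: it overlooks the time-point rows and the listing.

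A reader might also infer that the QT rows hide a QTcF signal or breach the protocol. They do neither. QTcF is tabulated against the same limits, the protocol sentence concerns clinical decisions, and Protocol 8.4.2 itself lists QT among the parameters to report. The QT rows add rate-driven flags and remove nothing.

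**Conclusion.** The point holds for one row. For the heart-rate decrease, the across-visit count registers only participants whose every post-baseline ECG qualifies. That follows from the wording and needs no assumption. The share captured, about 3% to 11% of participants with a decrease at either visit, rests entirely on the assumed means and SDs and on independent visit errors; other values would change the percentages but not the direction. Whether unscheduled ECGs are lost from the counts depends on a table convention that SAP 2.6.4.1 does not state; they would still be listed.

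The uncorrected-QT point is arithmetically right but is an optional tidying, not an error that masks anything.

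Severity is minor. SAP 2.6.1 plans no statistical analysis of safety and tolerability. The criteria in Protocol 9.1.4 do not refer to this table, and the dose review in Protocol 6.5.1 looks at the ECG data themselves.

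**What to change.** In SAP 2.6.4.1, state that the across-visit summary uses the maximum post-baseline value for increase and upper-limit categories and the minimum post-baseline value for the heart-rate decrease category, with unscheduled ECGs included in both.

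Optionally, apply the 450/480/500 ms and 30/60 ms limits to QTcF, and to QTcB if reported, and keep uncorrected QT in the descriptive summary that the section already plans.

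The cost is one line in the SAP and an edit to the table shell. No new data are needed.

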12.5.2 Safety endpoints

For all safety analyses, the safety set will be used. All listings and tables will be presented by treatment group.

Safety summaries (tables, figures) include data from Day 1 until the EOS with the exception of Baseline data which will also be summarized where appropriate (e.g. change from baseline summaries). In addition, a separate summary for death including on-treatment and post treatment deaths will be provided.

Adverse events

The number (and percentage) of participants with adverse events will be summarized in the following ways:

- by Primary system organ class and preferred term
- by Primary system organ class and preferred term and maximum severity

Separate summaries will be provided for ABO809 related AEs, SAEs, AESIs and deaths.

A participant with multiple AEs within a primary system organ class is only counted once towards the total of the primary system organ class.

Vital signs

All vital signs data will be listed by treatment group, participant, and visit/time and if ranges are available, abnormalities (and relevant orthostatic changes) will be flagged. Summary statistics will be provided by treatment and visit/time.

ECG findings

For ECG parameters, summary statistics for baseline value, actual assessment values, and change from baseline values will be presented by time of measurement. All ECG data will be listed; notably abnormal values will be flagged, and the overall interpretation of abnormality will be presented.

Clinical laboratory evaluations

Clinical laboratory data will include chemistry, hematology and urinalysis results up to EOS.

All laboratory values will be converted into International System of Units (SI) units. If grades are not defined by the Toxicity Grading Scale for Healthy Adult and Adolescent Volunteers Enrolled in Preventive Vaccine Clinical Trials (2007), results will be graded by the low/normal/high classifications based on laboratory normal ranges. Continuous laboratory data will be summarized by presenting summary statistics of raw data and change from baseline values (means, medians, standard deviations, ranges) by time point.

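### The two QT/QTc change-from-baseline rows in SAP 2.6.4.1 both exclude an increase of exactly 60 ms, so such a participant is counted in neither

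*SAP*

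**What the plan says.** SAP 2.6.4.1 (ECG and cardiac imaging data) plans a categorical ECG summary by "computing the number and percentage of participants at each time point and at the maximum post baseline value with following". For QT, QTcF or QTcB it lists five rows.

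- Three concern the absolute value: ">450 and ≤480 ms", ">480 and ≤500 ms", and above 500 ms.
- Two concern the change: "Increase from Baseline of ≥30 ms to <60ms" and "Increase from Baseline of >60 ms".

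The same section adds individual listings: "All ECG data will be listed; notably all newly occurring or worsening abnormalities as compared with baseline will be provided". It also says that abnormal values will be flagged.

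Protocol 12.5.2 sets no QTc change cut-offs. It plans that "summary statistics for baseline value, actual assessment values, and change from baseline values will be presented by time of measurement", together with a listing of all ECG data. The SAP section is therefore the only place where the change categories are defined.

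**The concern.** The lower change row stops short of 60 ms and the upper row starts beyond it, so the value 60 belongs to neither. A programmer who codes the rows as written will build in that gap. If the case arises, the number of participants with an increase of 30 ms or more, read by adding the two rows, is one too low at that time point. It may also be one too low in the maximum post-baseline summary. Someone would then have to decide where to place the participant after seeing the data.

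The absolute rows suggest a slip rather than a choice. They meet at 480 and 500 ms with no gap, so adjoining bands appear to have been intended.

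**Working it through.** The plan states no figure to reproduce. There are two checks: the category logic, and how often the gap would matter.

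**1. Category logic.** Write d for the increase from baseline in ms. The lower row is 30 ≤ d < 60 and the upper row is d > 60.

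| d (ms) | Lower row | Upper row |
|---|---|---|
| 29 | no | no |
| 30 | yes | no |
| 59 | yes | no |
| 59.9 | yes | no |
| 60 | no | no |
| 60.1 | no | yes |
| 61 | no | yes |

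Across every whole number from 30 to 200, 60 is the only increase that falls in no row. The absolute rows, checked from 451 to 700 ms, place each value in exactly one row.

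**2. When an absolute row still counts the participant.** With d = 60, the post-baseline value is baseline + 60. It exceeds 450 only if baseline exceeds 450 − 60 = 390 ms.

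| Baseline (ms) | Post-baseline (ms) | Change row | Absolute row |
|---|---|---|---|
| 380 | 440 | none | none |
| 390 | 450 | none | none |
| 391 | 451 | none | above 450 to 480 |
| 421 | 481 | none | above 480 to 500 |
| 441 | 501 | none | above 500 |

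A participant with a baseline of 390 ms or less is therefore in no QT/QTc row. One with a higher baseline is missing from the change rows only.

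**3. Frequency.** Inputs:

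- Scheduled post-dose ECGs: two per participant, on Days 10 and 28 (Protocol Table 8-1; the Day 1 ECG is before dosing).
- Participants: 30 planned, up to about 60 (Protocol section 3). That gives 60 to 120 post-dose ECGs.
- Assumptions not in the documents: changes are normal and centred on zero, their SD is 15 to 20 ms, and values are in whole milliseconds.

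The expected number of values at exactly 60 ms, per parameter, is N × [Φ(60.5/SD) − Φ(59.5/SD)], where N is the number of ECGs.

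| SD (ms) | Probability per ECG | N = 120 | N = 60 |
|---|---|---|---|
| 15 | 0.0000089 | 0.0011 | 0.0005 |
| 20 | 0.00022 | 0.027 | 0.013 |

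At these sizes the expected number is close to the chance of at least one. That chance is about 0.1% to 3% at 60 participants and about 0.05% to 1.3% at 30.

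**4. Effect of closing a boundary.** With 30 ≤ d ≤ 60 and d > 60, or with 30 ≤ d < 60 and d ≥ 60, every whole-number increase from 30 to 200 falls in exactly one row.

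**The case against.** The strongest reply is that very little depends on this table.

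- **The value stays visible.** All ECG data are listed. Change from baseline is summarised by time point, and SAP 2.1 includes the maximum among the summary statistics, so a largest increase of 60 ms would be printed. SAP 2.6.4 adds boxplots. This stands.
- **A reader might infer that the participant disappears from the outlier table.** The documents do not support that in general, because anyone whose post-baseline value exceeds 450 ms is still in an absolute row.
- **A reader might infer that the rows should add up and do not.** They were never a full partition. Increases below 30 ms and values of 450 ms or less have no row, and one participant can be in both an absolute and a change row. The defect is narrower: the two change rows do not cover every increase of 30 ms or more.
- **A reader might infer that a participant at a safety threshold is missed.** Neither document attaches an action to a 60 ms increase. Protocol 9.1.4 has no QTc stopping criterion, and Protocol 8.4.2 handles an ECG safety concern through repeat ECGs and review, not through this table.
- **QTcF need not be a whole number.** Protocol 8.4.2 derives it as QT divided by the cube root of RR, and no rounding rule is stated. If decimals are kept, exactly 60 is rarer still. This stands.
- **The sign before 60 may be a typographical or conversion slip for ≥.** That cannot be excluded from the text alone. However, the signs before 30, 480 and 500 in the same list read sensibly, so nothing points to it.

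These points limit the consequence. None of them puts 60 ms into a row.

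**Conclusion.** The gap is real, and nothing elsewhere in the protocol or SAP closes it. It applies to QT, QTcF and, if reported, QTcB. When the case arises, the effect is one participant missing from the change rows at the time point concerned or at the maximum.

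The logical finding needs no assumptions beyond the printed signs. The frequency does: it rests on the assumed SD, the centring on zero and whole-millisecond recording, and its upper figure also needs the full 60 participants. This is a minor correction to a descriptive safety table, with no bearing on the primary analysis or on any dosing decision rule in the documents.

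**What to change.** Change one sign in SAP 2.6.4.1. Either start the upper row at ≥60 ms or end the lower row at ≤60 ms. Both make the two rows cover every increase of 30 ms or more without overlap. It would help to state, in the same place, whether QTcF and QTcB are rounded before they are categorised.

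The cost is one character in the SAP and one in the table program. It should be done before database lock, so that no boundary case is placed after it has been seen.
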